4.5.1 Dose Delays

Patients who experience toxicity that is potentially dose-limiting should have study drug held pending assessment, management, and resolution of the toxicity. Specific guidance for the management of known toxicities associated with pembrolizumab and margetuximab treatment, including infusion-related reactions, immune-related adverse events (irAEs), and cardiotoxicities of special interest is provided in [Section 6.5](#). For patients in whom the toxicity is assessed to be unrelated to study drug or for whom the toxicity does not meet the criteria for DLT or meet criteria for the known toxicities, therapy may be re-instituted at the same dose and schedule that was administered prior to the event, presuming the toxicity has resolved to \leq Grade 1 in severity. Reinstitution of therapy shall be conducted as follows:

- For patients in whom the toxicity is assessed to be related to study drug, dose delays of up to 14 days are allowed (see exception for cardiotoxicities of special interest described in [Section 6.5.3](#)). This may include up to one missed dose. However, the procedures at the original scheduled missed visit should be performed as soon as possible and resumed as Day 1 of next cycle with treatment reinstated after recovery from toxicity.
- For patients in whom the toxicity is assessed to be related to study drug, dose delays $>$ 14 days will result in discontinuation of treatment (see exception for cardiotoxicities of special interest described in [Section 6.5.3](#)).

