6.5.2.7 Thyroid Toxicity

Thyroid disorders can occur at any time during treatment with pembrolizumab. Monitor patients for changes in thyroid function per protocol and as indicated based on clinical evaluation and for clinical signs and symptoms of thyroid disorders. Isolated hypothyroidism may generally be managed with replacement therapy without treatment interruption and without corticosteroids, and a suggested treatment guideline for hyperthyroidism is described below:

- Grade 1 hyperthyroidism
 - No specific therapy required
- Grade 2 hyperthyroidism
 - Hold pembrolizumab and margetuximab
 - Consider starting oral corticosteroid therapy
 - Resume pembrolizumab and margetuximab if corticosteroid dose is reduced to ≤ 10 mg prednisone or equivalent per day and stable on hormone replacement therapy (if necessary).
- Grade 3 or 4 hyperthyroidism
 - Hold pembrolizumab and margetuximab
 - Consider hospitalization and consulting endocrinologist
 - Begin IV corticosteroids such as methylprednisolone 2-4 mg/kg IV (or equivalent) divided twice daily
 - Initiate hormonal replacement as necessary
 - May consider restarting pembrolizumab and margetuximab with complete resolution or stable on hormone replacement therapy within 14 days

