7.6 Clinical Laboratory Tests

Blood and urine samples will be collected at the times specified in [Appendix 1](#) and [Appendix 2](#). Hematology, chemistry, pregnancy, urinalysis, coagulation time, and endocrine evaluation tests will be performed locally. Safety labs should be performed and reviewed before study drug administration.

Please consult the Laboratory Manual for specific directions on collection and processing samples.

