7.10.3 Pharmacokinetics

Serum concentrations of margetuximab will be monitored using a quantitative sandwich ELISA. Single and multiple dose PK parameters for margetuximab (e.g., C_{max} , T_{max} , AUC_{tau} , AUC_{inf} , C_{trough} , CL , V_{ss} , and T_{half}) will be derived from margetuximab serum concentration versus time data. Population PK analyses may be conducted using data from this study alone or combined with data from other studies.

Blood samples for margetuximab PK will be collected at the following time points given in the table below. Blood samples will be collected from the arm contralateral to the site of IV infusion. If an indwelling catheter is used, the fluid in the catheter will be removed and discarded prior to the collection of blood sample for ADA or PK assessment.

Table 6 Pharmacokinetics Blood Sampling Schedule for Margetuximab

Tumor Assessment Cycle	Treatment Day of Cycle	Pembrolizumab /Margetuximab Dose Number ^{a, b}	PK Sampling Time After the end of Infusion (hr)	PK Sample Collection for Margetuximab	
				Dose Escalation	Cohort Expansion
Initial (1 st)	1	1	0 (Predose) ^c	X	X
			EOI ^d	X	X
			5 ^g	X	X
	2		24 ^g	X	NA
	8		NA ^h	X	NA
2 nd	1	2	0 (Predose) ^e	X	X
			EOI ^d	X	X
3 rd	1	3	0 (Predose) ^e	X	X
			EOI ^d	X	X
	2		24 ^g	X	NA
5 th & 7 th Cycle	1		0 (Predose) ^e	X	X
			EOI ^d	X	X
EOTV	NA ^f	EOTV (28 days after the last dose of study drug)	NA ^f	X	X

- a Pembrolizumab dose and margetuximab dose administered as 0.5 hour (30 min) and 2-hour (120 min) infusions, respectively.
- b Margetuximab may be administered the day following pembrolizumab administration for safety reasons or scheduling purposes.
- c Predose PK sample on Study Day 1 (Treatment Day 1 of Initial [1st] Cycle) will be collected prior to margetuximab infusion; ADA sample for this time point will be collected prior to margetuximab infusion.
- d EOI= end of margetuximab infusion; sample will be collected within 5 min to the end of infusion.
- e All other predose PK samples will be collected prior to margetuximab infusion simultaneously with ADA sample.
- f Not applicable as this is for the end of treatment visit (EOTV); however, PK sample will be collected simultaneously with ADA sample.
- g These times are noted from margetuximab end of infusion. If there are delays in margetuximab infusion, these time points will be at 5, and 24 hours post end of margetuximab infusion, respectively.

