7.12 Appropriateness of Measurements

Routine laboratory evaluations including hematology, chemistry, coagulation, and urinalysis will be carried out in local institutional laboratories. Additional local safety laboratory assessments may be used to supplement the protocol-prescribed assessments and may be used to elucidate certain AEs.

Serum concentrations of margetuximab will be monitored using an ELISA based assay. Standard bridging ELISAs will be carried out in the Sponsor's designated central laboratory to characterize the immunogenicity of margetuximab. Analysis of PK data will be carried out using industry standard software. Population PK modeling may be performed and an appropriate model and model parameters may be described.

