8.3 End of Treatment Visit

A list of evaluations to be performed for the End of Treatment visit is provided in [Appendix 1](#) and [Appendix 2](#). Criteria for triggering the End of Treatment visit are specified in [Section 5.3](#). The End of Treatment Visit should be performed after the patient has met off-treatment criteria and End of Study should be noted after patient has been followed for at least 28 days after the last dose of study drug depending on ability to follow the patient and duration and severity of ongoing AEs. It is recognized that certain patients (such as those experiencing progression of disease) may be cared for in facilities other than the participating investigational site, may proceed to receive other cancer therapy, and/or may elect not to return to the investigational site. Therefore, this visit is considered optional, but should be carried out whenever possible.

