Appendix 2 Time and Events Schedule: Cohort Expansion Phase (Parts B – C)

Evaluation/Procedure ¹	Screening	Cycle 1	Cycle 2	Cycle 3	Cycle 4 - 35	End of Treatment Visit	Follow-Up Visits
	Day -28 to 0	Day 1	Day 1	Day 1	Day 1		
Study Drug Administration ²							
Pembrolizumab		x	x	x	x		
Margetuximab		X	x	x	x		
Eligibility							
Informed consent ³	x						
Patient registration		X					
HER2 status testing ³	x						
Medical history	x						
Review of concomitant medications	x	X	x	x	x	x	
ECOG performance status	x	X	x	x	x	x	
ECG ⁴	x	X		x	x	x	
MUGA or Echocardiography ⁵	x			x	x	x	
β-hCG pregnancy test ⁶	x						
Archival biopsy specimen	x						
Fresh Pre- and On-Treatment Tumor Biopsy ^{20, Appendix 1}		x ²⁰	x ²⁰				

Evaluation/Procedure ¹	Screening	Cycle 1	Cycle 2	Cycle 3	Cycle 4 - 35	End of Treatment Visit	Follow-Up Visits
	Day -28 to 0	Day 1	Day 1	Day 1	Day 1		
Safety & Pharmacodynamic Evaluation							
Physical examination ⁷	x	X	x	x	x	x	
Monitor for Adverse Events			Continuous				
CBC with differential, platelet count ^{8, 12}	x	X	x	x	x	x	
Chemistry panel ^{8, 12, 13}	x	X	x	x	x	x	
Free T4 and TSH ^{8, 12}		X	x	x	x		
PT; aPTT ^{8, 12}		X	x	x	x		
Urinalysis ^{8, 12}	x	x	x	x	x	x	
HER2-specific immune responses (PBMC, plasma, ctDNA) ⁹		x			x	X	
Flow cytometry: Lymphocyte subsets, NK cells and activation markers ¹⁰		x	x	x	x	X	
Fc receptor genotyping ¹¹		x					
Serum Cytokine sampling ¹⁴		x					
Vital signs (pulse, respirations, blood pressure, temperature) ¹⁵	x	X	x	x	x	X	
Therapeutic Activity							
Disease assessment by RECIST and irRC: CT/MRI chest, abdomen and pelvis ¹⁶	x			x	x ¹⁶	X	x ¹⁶
CT/MRI Brain ^{16, 17}	x			x	x ^{16, 17}	X	
Pharmacokinetics/Immunogenicity							
Margetuximab PK sampling ¹⁸		X	x	x	x ¹⁸	X	

Evaluation/Procedure ¹	Screening	Cycle 1	Cycle 2	Cycle 3	Cycle 4 - 35	End of Treatment Visit	Follow-Up Visits
	Day -28 to 0	Day 1	Day 1	Day 1	Day 1		
ADA blood sample (anti-margetuximab antibodies) ¹⁹		X	x	x	x ¹⁹	X	
Contacts							
Telephone, Electronic Contact, or office visit							x

- 1 Visits occur ± 3 days of scheduled visit, with exception of Cycle 1 Day 1 and unless otherwise noted.

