- 2 Pembrolizumab must be administered first. An effort should be made to begin the margetuximab infusion between 30 minutes to 60 minutes after the completion of the pembrolizumab infusion. It is understood that this window may not always be attainable, but it is the preferred window of time to administer margetuximab. Margetuximab may be administered the next day for safety reasons or scheduling purposes. The start and stop time of each pembrolizumab and margetuximab infusion must be documented.
- 3 To be obtained before registration (no time constraint).
- 4 **Timing of ECGs in relation to pembrolizumab:**
 - Expansion**
 - Cycles 1, 3, 5, and 7 ECGs will be obtained before pembrolizumab infusion (up to 3 minutes before the infusion [pre-dose] and at 30 minutes (end of infusion) on Day 1
 - End of Treatment ECGs will be obtained at no specific time.
 - Timing of ECGs in relation to margetuximab:**
 - Expansion**
 - Cycles 1, 3, 5, 7 ECGs will be obtained at 120 minutes (end of infusion) on Day 1 of each cycle.
 - End of Treatment ECGs will be obtained at no specific time.
- 5 MUGA or echocardiography to be performed on Day 1 (or 3 to 4 prior to Day 1) of every other cycle for 6 months; thereafter, these assessments may be performed every 4 cycles.
- 6 For women of childbearing potential, to be obtained within 72 hours prior to initial dose of pembrolizumab. **For Canadian patients only:** Female patients of childbearing potential must have a negative pregnancy test prior to every cycle of pembrolizumab.
- 7 Includes height (baseline only) and weight. Note that full physical exams to be done on Screening Day (baseline) and at the EOTV. All other physical exams will be directed physical exams based on patient symptoms, tumor location and as clinically indicated.
- 8 Sample will be collected prior to pembrolizumab infusion; CBC with differential, platelet count, Chemistry panel, Free T4 and TSH, PT and aPTT, and Urinalysis may occur up to 72 hours in advance of the Day 1 infusion day of each treatment cycle.
- 9 Blood for HER2-specific immune response to be drawn pre-pembrolizumab infusion on Cycle 1, Day 1; Cycle 4, Day 1; and at End of Treatment Visit.
- 10 Blood for Flow Cytometry assays to be drawn on Day 1 at pre-pembrolizumab infusion for Cycle 1 to Cycle 6, inclusive, and lastly at End of Treatment Visit.
- 11 Fc receptor genotyping to be drawn only once on Day 1 of Cycle 1 pre-pembrolizumab infusion.

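### Free T4 and TSH are drawn before each dose but not at the End of Treatment Visit, so no thyroid test is scheduled after the last dose; adding them to the chemistry tube already taken there is a minor, cheap improvement

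*Protocol*

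**What the plan says.** Protocol Appendix 2 lists "Free T4 and TSH" on Day 1 of Cycles 1, 2, 3 and 4–35. The row is blank at Screening, at the End of Treatment Visit and at follow-up. Blood count, chemistry panel and urinalysis are all marked at End of Treatment.

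Footnote 8 of that appendix fixes the timing: "Sample will be collected prior to pembrolizumab infusion; CBC with differential, platelet count, Chemistry panel, Free T4 and TSH" and the other listed laboratory tests may be taken up to 72 hours ahead of the Day 1 infusion. Section 7.6 adds: "Safety labs should be performed and reviewed before study drug administration".

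Appendix 4 leaves the thyroid row blank at End of Treatment while listing a 4 mL chemistry tube there. Its first footnote says the thyroid tests need no extra blood because they are added to the chemistry request. Appendices 1 and 3 (Part A) have the same layout.

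Outside the schedule, Section 6.5.2.7 says: "Monitor patients for changes in thyroid function per protocol and as indicated based on clinical evaluation". Section 7.12 says: "Additional local safety laboratory assessments may be used to supplement the protocol-prescribed assessments". Section 4.5.1 covers doses delayed for drug-related toxicity: "the procedures at the original scheduled missed visit should be performed as soon as possible".

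Table 6 in Section 7.10.3 places the End of Treatment Visit at "EOTV (28 days after the last dose of study drug". Section 8.3 says of attendance: "Therefore, this visit is considered optional, but should be carried out whenever possible".

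**The concern.** Every scheduled thyroid sample precedes a dose, so the effect of the final dose is never followed by a scheduled test. Section 6.5.2.7 treats thyroid disorder as a toxicity in its own right that may arise at any point on pembrolizumab. It sets out replacement therapy for hypothyroidism and graded management for hyperthyroidism. Section 2.5.1.1 reports that peripheral target engagement lasts beyond 21 days, and Section 7.9.1 continues general adverse-event collection for up to 28 days after the last dose. No thyroid test is planned in that window.

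What is at stake is limited to biochemical change that is silent or appears late. A patient with symptoms should be picked up by the full physical examination, vital signs and adverse-event review at End of Treatment. No efficacy analysis or sample-size figure is touched.

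**Working it through.** The plan states no figure for this point. The check is a reading of the tables plus simple sums.

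**1. Is the omission real?** Four tables (Appendices 1 to 4) leave the thyroid row blank at End of Treatment, so a damaged table is an unlikely explanation. The chemistry panel does not cover it by implication: footnote 13 of Appendix 2 lists the analytes and includes neither TSH nor free T4, and Table 4 in Section 7.6.1 puts the endocrine tests in a separate group. The follow-up column carries no laboratory tests.

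**2. When could a value after the last dose still exist?**
- A next-cycle sample is drawn before the dose, and the dose is then withheld (Section 7.6; Appendix 2, footnote 8).
- The missed-visit procedures are carried out after a delay for drug-related toxicity (Section 4.5.1).
- Testing is clinically indicated (Sections 6.5.2.7 and 7.12).

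Two kinds of patient have no scheduled value after their last dose. One who stops after a single dose without a Cycle 2 draw has no scheduled post-baseline value at all. One who completes Cycle 35 has no later cycle visit.

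**3. How long is the gap?** Assume 21-day cycles and End of Treatment 28 days after the last dose (Table 6).
- Cycle 35 completer, sample on Day 1: 28 days. Sample taken 72 hours early: 28 + 3 = 31 days.
- Next-cycle sample on its Day 1 with the dose withheld: 28 − 21 = 7 days. Sample taken 72 hours early: 7 + 3 = 10 days.

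Footnote 1 of Appendix 2 allows visits to move by 3 days either way. If that applies to End of Treatment, the first range becomes 28 − 3 = 25 to 31 + 3 = 34 days, and the second becomes 7 − 3 = 4 to 10 + 3 = 13 days. The Day 1 window would widen the second range further. A visit held sooner after stopping shortens every gap.

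**4. Does the fix need more blood?**
- End of Treatment volume as tabulated (Appendices 3 and 4): blood count 2 + chemistry 4 + flow cytometry 5 + PK 3 + ADA 3 + HER2 immune response 24 = 41 mL, which matches the stated total.
- Where thyroid tests are already scheduled (Appendix 4, Cycle 1 Day 1): 2 + 4 + 3 + 5 + 9 + 3 + 8.5 + 24 = 58.5 mL, again the stated total, with the thyroid tests contributing 0 mL.
- Adding them at End of Treatment therefore leaves that visit at 41 + 0 = 41 mL.

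**The case against.** The strongest reply is that this is a preference. Four tables agree and PT/aPTT is laid out the same way, so the omission looks deliberate and breaks no rule. That is right, and the point is offered only as an improvement to a design choice. PT/aPTT differs in one respect: it would need its own 3 mL tube, while the thyroid tests need none.

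A second reply is that a silent change has little consequence. Grade 1 hyperthyroidism calls for no treatment, immune-related events of special interest start at Grade 3 (Section 7.9.3), and no dosing decision remains. SAP Section 6.7.2 names hematology, chemistry and urinalysis panels but no endocrine panel. This limits the value of the extra result but does not remove it, because hypothyroidism and higher-grade hyperthyroidism remain treatable after the last dose.

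A third reply is that few patients would gain. A Cycle 35 completer already has 35 scheduled samples. Such patients may be uncommon: the background sections cite a median PFS of 1.9 months and a median exposure of 2.1 months on pembrolizumab alone, though these come from other studies and are only indicative. A one-dose patient may not attend an optional visit. A patient found to have progressed at a scheduled scan may already have had the next-cycle sample, since scans fall within 3 days before Day 1 and laboratory tests within 72 hours. All of this stands, and it is why the point is minor.

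Finally, four tables must be amended across approximately 29 institutions, with ethics approval where required (Section 11.1). That also stands and bears on how the change should be made.

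**Conclusion.** The point holds as a minor improvement. No thyroid test is scheduled after the final dose in any part of the study, and the other routes to one depend on a withheld dose, a toxicity delay or a clinical prompt. The nominal gap before End of Treatment is 28 to 31 days for a Cycle 35 completer and 7 to 10 days where a next-cycle sample was drawn and dosing withheld. Both ranges assume 21-day cycles and a visit 28 days after the last dose, and both widen if the 3-day visit window applies. The documents do not say how many patients fall in each group, and no event rate or bias is claimed. The benefit is confined to silent or late biochemical change in patients who attend.

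**What to change.** Mark Free T4 and TSH at the End of Treatment Visit in Appendices 2 and 4, run on the chemistry tube already drawn there. Make the same change in Appendices 1 and 3 for consistency and for any Part A patient still on treatment.

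The running cost is one local assay pair per attending patient, with no added visit or tube. Those affected are up to 25 Part C patients plus anyone still on treatment among those enrolled earlier. Section 2.3.1.1 gives 64 treated in this study by 30 September 2017; the number still on treatment is not stated.

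The administrative cost is the amendment itself, with any schedule and eCRF updates and ethics approvals that follow. The change does not justify a standalone amendment and should go into the next one made for other reasons.

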6.3 Study Drug Administration

Note: Dosing interruptions are permitted in the case of medical/surgical events or logistical reasons (i.e. elective surgery, unrelated medical events, patient vacation, holidays, etc.) not related to study therapy.

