6.5.2.2 Hepatic Toxicity

6.5.2.2.1 Elevations in Transaminases

Management guidelines for patients experiencing hepatic toxicity are as follows:

- Grade 1 elevations
 - No specific therapy required
- Grade 2 elevations
 - For elevations in transaminases 3 to 5 \times ULN (Grade 2), rule out viral and other etiologies, and consider immediate oral steroids such as prednisone 60 mg/day divided twice daily, and hold pembrolizumab and margetuximab.
 - If improvement to \leq Grade 1 does not occur within 48 hours with oral steroids, consider IV steroids such as methylprednisolone at 2 mg/kg/day divided twice daily or oral steroids such as prednisone 60 to 120 mg per day, divided twice daily

- Resume pembrolizumab and margetuximab at the next scheduled dose if:
 - No more than one dose of pembrolizumab and margetuximab was missed
- If improvement to \leq Grade 1 does not occur within 14 days, discontinue pembrolizumab and margetuximab.
- Grade 3 elevations
 - Discontinue pembrolizumab and margetuximab
 - Initiate IV steroids and,
 - If no response to corticosteroid therapy within 3 to 5 days is observed, consider adding immune suppression therapy with mycophenolate. Do not use infliximab in these cases because of a potential for autoimmune hepatitis (40).
 - Monitor liver function tests at least twice weekly (or more frequently as clinically appropriate in the judgment of the investigator) until transaminases have returned to Grade 1 or baseline.
- Grade 4 elevation
 - Discontinue pembrolizumab and margetuximab
 - Treat as for Grade 3 elevation.

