6.8 Concomitant Therapy

Margetuximab and pembrolizumab are the only anti-cancer drugs to be administered routinely in this study. No concomitant anti-cancer therapy will be given with exception of adjuvant hormonal therapy for treatment of patients with breast or prostate cancer. All concomitant medications and blood products administered during the patient's participation in the study until the post treatment follow-up visit must be recorded in the source document and on the electronic Case Report Form (eCRF). All changes in infusions, including interruptions and their duration as well as reductions in rate and duration must be recorded.

The following rules concerning concurrent treatment(s) will apply in this study:

- Any other anti-neoplastic therapies including but not limited to chemotherapy or other small molecules, biologics, or radiotherapy are not allowed. For patients who require palliative radiotherapy (i.e., cumulative dose less than 3000 rads, limited field of distribution) for reasons other than disease progression, therapy with margetuximab and/or pembrolizumab may be interrupted for up to 4 weeks. Palliative radiotherapy may not be given concurrently with either margetuximab or pembrolizumab. Treatment with palliative therapy should be initiated at least 24 hours after receiving either margetuximab or pembrolizumab, and re-initiation of margetuximab or pembrolizumab can begin seven (7) days after the completion of palliative radiotherapy if there were no complications associated with the radiotherapy. Palliative radiotherapy fields also should not overlap tumor lesions that have previously been designated as target lesions. In the event that this is medically necessary for palliative purposes, the patient may continue on study, but will no longer be evaluable for objective response from the time palliative radiotherapy is initiated.
- Patients may not receive other investigational drugs during the period of study participation.

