7.10 Efficacy, Immunogenicity, Pharmacokinetic, and Pharmacodynamic Assessments

7.10.1 Efficacy Assessments

7.10.1.1 Radiologic Evaluation: Treatment of Patients According to Principles of Immune-Related Response Criteria

Tumor assessments will be obtained at screening using CT and/or MRI scans at time intervals as specified in the [Appendix 1](#) and [Appendix 2](#) (Time and Events Tables). Radiographic disease assessments will occur every 6 weeks (i.e., following 2 cycles of treatment [specifically prior to Cycles 3, 5, 7, etc.]) for the first 24 weeks and then every 12 weeks thereafter until documented progression, initiation of alternative anti-cancer therapy, lost to follow up, withdrawal of informed consent, death, or end of study. Treatment will continue until patients have completed study therapy and required follow-up, experienced disease progression according to irRC, or have been withdrawn from the study (see [Section 4.4](#) and [Section 5.3](#)). At each on-treatment tumor assessment time point, the objective response status will be determined. In the context of the statistical analysis for this trial, objective response determination and the assessment of best overall response (BOR) will be defined using both conventional RECIST 1.1 criteria ([Appendix 7](#)) as well as an adaptation of these criteria, designated as immune-related response criteria (irRC) ([Appendix 8](#)). Patient management decisions, however, will be made solely based on the immune-related response criteria.

For patients who demonstrate acceptable tolerability of treatment with pembrolizumab and margetuximab and achieve an objective response assessment of irCR, irPR or irSD, or unconfirmed clinically stable irPD, therapy may be continued (see [Section 4.4](#) and [Section 5.3](#)).

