- 12 Samples will be analyzed by the local laboratory.
- 13 Includes ALB, ALK-P, ALT, AST, amylase, bicarbonate, BUN, Ca, Cl, creatinine, glucose, lipase, magnesium, phosphorus, K, Na, total protein, uric acid, total and direct bilirubin.
- 14 For Cytokine samples: Samples can be obtained selectively at additional time points in patients who experience an adverse event with signs and symptoms of cytokine release, with the goal to obtain a cytokine sample immediately at the time of onset of adverse event. Multiple cytokine samples can be drawn for any specific adverse event that is suspected to be due to cytokine release, as clinically indicated; specific date and times of blood draws must be recorded. Separate cytokine samples should be drawn for each adverse event suspected of cytokine release, with specific date and time of draw to be recorded.
- 15 Vital signs include temperature, pulse, blood pressure, and respiratory rate and are obtained as follows:
 - In relation to pembrolizumab infusions on Days 1: Vital signs will be taken immediately before the pembrolizumab infusion (up to 5 minutes before the infusion [pre-dose]); at 15 minutes after the start of infusion; at 30 minutes (end of infusion), and at 1 hour after infusion if the margetuximab dose has not already commenced.
 - In relation to margetuximab infusions on Days 1: Vital signs will be taken immediately before margetuximab infusion (up to 5 minutes before the infusion [pre-dose]), at 60 minutes after start of infusion, at 120 minutes (end of infusion), and at 1 hour after the completion of infusion.
 - Note: For subsequent cycles after Cycle 1; the 1-hour post-infusion vital signs measurements may be deferred if continuing monitoring is not clinically indicated.
- 16 Radiographic disease assessments will occur every 6 weeks (i.e., following 2 cycles of treatment) for the first 24 weeks and then every 12 weeks thereafter until documented progression, initiation of alternative anti-cancer therapy, lost to follow up, withdrawal of informed consent, death, or end of study. To be performed within 3 days prior to dosing on Day 1 of every other cycle for the first 24 weeks (specifically prior to Cycles 3, 5, 7, and 9) and then every 4th cycle (prior to Cycles 13, 17, 21, etc.). Disease assessment will be done at office follow-up visits until end of study if patient agrees.

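### Scans are tied to dosing days, so a permitted dose delay can move the second scan past the 3-month PFS landmark; the effect is small and a fixed calendar removes it

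*Protocol*

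**What the plan says.** **Scan schedule.** Footnote 16 in both appendices opens with a calendar interval: "Radiographic disease assessments will occur every 6 weeks (i.e., following 2 cycles of treatment". It then gives the working instruction: "To be performed within 3 days prior to dosing on Day 1 of every other cycle for the first 24 weeks", naming Cycles 3, 5, 7 and 9, and every fourth cycle after that. Protocol 7.10.1.1 pairs the two in the same way: "every 6 weeks (i.e., following 2 cycles of treatment [specifically prior to Cycles 3, 5, 7, etc.]) for the first 24 weeks". The Synopsis, Protocol 4.1.1 and SAP 3.1 repeat the pairing.

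**Permitted delays.**
- Protocol 4.5.1, for drug-related toxicity: "dose delays of up to 14 days are allowed", which may include one missed dose. The missed visit's procedures are to be done promptly, and the schedule is "resumed as Day 1 of next cycle with treatment reinstated after recovery from toxicity".
- Protocol 6.3, for unrelated medical or logistical reasons: "Dosing interruptions are permitted in the case of medical/surgical events or logistical reasons". No maximum is given.
- Protocol 6.8, for palliative radiotherapy: "therapy with margetuximab and/or pembrolizumab may be interrupted for up to 4 weeks".
- Protocol 6.5.2.2.1 words the restart differently: "Resume pembrolizumab and margetuximab at the next scheduled dose if" at most one dose has been missed. Sections 6.5.2.3 to 6.5.2.5 have similar restart rules.

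**PFS.** SAP 5.1.2 converts days to months by dividing by 365.25/12, counting the first-dose date as Day 1. SAP 6.6.2.1 plans Kaplan-Meier PFS rates at 3 and 6 months.

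**The concern.** The six-week interval and the dosing link agree only while every dose is on time. Once a dose is late, a site following the working instruction scans when the patient is dosed, and no passage holds later scans to the calendar. The instruction in 4.5.1 to catch up on missed procedures covers related toxicity only. It does not name scans or date the later ones.

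Radiographic progression is dated by the scan that shows it. The second scan is planned about a week before the 3-month landmark, so a two-week shift can carry it across. Progression dating then depends partly on toxicity, and on how a site numbers the cycle at which treatment resumes. What is at stake is the 3-month PFS rate.

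**Working it through.** **Nominal days.** Cycles last 21 days, so Cycle k starts on Day 1 + 21(k − 1). Cycles 3, 5 and 7 start on Days 43, 85 and 127, which reproduces Protocol Table 5; Cycle 9 starts on Day 169. The second scan, 0 to 3 days before Cycle 5, is due on Day 82–85, or Day 79–88 allowing for the ±3-day visit window in footnote 1.

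**Landmarks.** One month is 365.25/12 = 30.4375 days, so 3 months is Day 91.3 and 6 months is Day 182.6.

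**Second scan after an interruption before Cycle 5.**

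| Situation | Cycle 5 | Second scan | Months |
|---|---|---|---|
| No delay | Day 85 | Day 82–85 | 2.69–2.79 |
| 14-day delay at Cycle 2, 3 or 4; later cycles move | 85 + 14 = 99 | Day 96–99 | 3.15–3.25 |
| 14-day delay; missed cycle number skipped (Cycle 2 due Day 22, resumed Day 36 as Cycle 3) | 36 + 42 = 78 | Day 75–78 | 2.46–2.56 |
| Dose skipped to the next scheduled one (a 21-day gap) | Day 85 | Day 82–85 | 2.69–2.79 |
| 4-week radiotherapy interruption counted from the last dose (Day 64); later cycles move | 64 + 28 = 92 | Day 89–92 | 2.92–3.02 |
| 4-week radiotherapy interruption counted from the due date; later cycles move | 85 + 28 = 113 | Day 110–113 | 3.61–3.71 |

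A delay at Cycle 3 or 4 with the cycle number skipped also gives Day 78. In the radiotherapy case counted from the last dose, only Day 92 crosses the landmark.

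**Effect on a delayed patient when later cycles move.** Assume exponential PFS and progression seen only at scans. The median runs from 1.9 months (pembrolizumab monotherapy, Protocol 2.2.1) to 2.6 months (top of the weekly paclitaxel range, Protocol 2.1.2). The chance of counting as progression-free at 3 months is S(t) = 2^(−t/median), where t is the time from first dose to the last scan before Day 91.3.

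| Last scan before the landmark | t (days) | Median 1.9 | Median 2.6 |
|---|---|---|---|
| On time, Day 85 | 84 | 0.365 | 0.479 |
| Delay at Cycle 2 or 3: first scan Day 57, second Day 99 | 56 | 0.511 (+0.146) | 0.612 (+0.133) |
| Delay at Cycle 4: first scan Day 43, second Day 99 | 42 | 0.604 (+0.239) | 0.692 (+0.213) |

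If the catch-up instruction in 4.5.1 kept the first scan near Day 43 after a Cycle 3 delay, that case would join the bottom row. If the cycle number is skipped, t = 77 and S is 0.397 or 0.509, about +0.03, because the next scan is not until Cycle 7 on Day 120. If treatment resumes at the next scheduled dose, the change is zero.

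**Deaths.** These count on the day they occur. If 10% to 30% of early events are deaths (assumed), the range for moved cycles becomes 0.133 × 0.7 = 0.093 to 0.239 × 0.9 = 0.215.

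**Effect on the cohort.** If 10% to 20% of patients are delayed the full 14 days (assumed; not in the documents), the rate rises by 0.10 × 0.133 = 1.3 points to 0.20 × 0.239 = 4.8 points, before any allowance for deaths. The 95% half-width at n = 30 is 1.96 × √(p(1 − p)/30), or 17.5 points at p = 0.4 and 17.9 at p = 0.5.

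**Six months.** With later cycles moved 14 days, Cycle 9 is on Day 183 and its scan on Day 180–183 (5.91–6.01 months). Only a scan on the dosing day itself crosses Day 182.6.

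**The case against.** Footnote 16 can fairly be read as one rule: the dosing-linked instruction governs, and six weeks is only its nominal spacing. Much of that stands. If the calendar governed, the scan would stay at Day 82–85, so the spread comes from the dosing link and cycle numbering rather than from two anchors as such. But accepting the dosing rule confirms that delays move scans. It does not fix the day either, since the restart wording in 4.5.1 differs from that in 6.5.2.

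A reader might infer more than the documents support:
- **That Day 75 to Day 99 bounds the second scan.** It illustrates one 14-day delay. Radiotherapy can take the scan to Day 113, and 6.3 sets no limit.
- **That PFS is biased in one direction.** The scan can move earlier, later or not at all, depending on the reading.
- **That response rate or response duration is affected.** Nothing in the calculation shows this.

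Timing also limits the benefit. Protocol 2.3.1.1 reports 64 patients already treated in this study by 30 September 2017, and Protocol 9.2 describes the Part B futility look as past. New wording mainly helps Part C, of up to 25 patients, whereas the 30-patient precision figure describes a Part B region.

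The SAP's existing PFS sensitivity analysis does not answer the point. It changes which late events count, not the date given to a progression found at a delayed scan.

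**Conclusion.** The point holds as a small, correctable weakness. The dosing-linked rule allows a toxicity-related delay to carry the second scan across the 3-month landmark, and no passage prevents it. Where later cycles move, the gain per delayed patient is about 13 to 15 points for a delay at Cycle 2 or 3 and 21 to 24 points for one at Cycle 4, less if some early events are deaths. On the cohort rate it is at most about 1 to 5 points, well inside the sampling uncertainty.

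These sizes rest on exponential PFS with historical medians, detection only at scans, and an assumed share of patients delayed the full 14 days. The endpoint is secondary and descriptive, so no error rate is involved. Priority is low.

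**What to change.** State that scans are due on Study Days 43, 85, 127 and 169, then every 84 days, counted from first dose (Day 1), within 3 days, and are not moved by dose delays or interruptions. Even 3 days late, the second and fourth scans then fall on Day 88 (2.89 months) and Day 172 (5.65 months), before both landmarks however 4.5.1 is read. Section 4.5.1 can stay as it is.

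Make the change in footnote 16 of Appendices 1 and 2 and in Protocol 7.10.1.1. Conform the Synopsis (general study design, treatment and study duration, efficacy assessments), Protocol 4.1.1 and SAP 3.1; otherwise the cycle-linked wording left there would contradict the new rule.

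For scans already done, which covers most of Part B, one PFS-only sensitivity analysis could be added to SAP 6.6.2.1. It would date a progression found more than 3 days late at that scan's due date. This is optional and uses dates already collected.

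The cost is a wording amendment and no extra patients. The downside is that some scans will not coincide with a dosing visit.
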